## 2.0 TRIAL DESIGN

### 2.1 Trial Design

This is a non-randomized, multi-site, 2-arm, open-label trial of MK-1248 monotherapy (Arm 1) and MK-1248 in combination with pembrolizumab (Arm 2) in subjects with a histologically or cytologically confirmed diagnosis of any type of solid tumor who have measurable disease.

This trial will use an adaptive design based on the pre-specified criteria of dose limiting toxicity (DLT). For Dose Escalation (Parts B and D) a 3+3 dose escalation design will be utilized (See Section 5.2.1.4). For Dose Confirmation (Parts C and E) the toxicity probability interval (TPI) design [1] will be utilized to refine the estimate of maximum tolerated dose (MTD).

In Arm 1, MK-1248 monotherapy, dose escalation will begin with 2-subject cohorts (Part A) starting at a MK-1248 dose of 0.12 mg and will proceed based on adverse events to a dose of 10.0 mg or until a DLT occurs. If a DLT occurs, an additional subject will be enrolled and the rules of 3+3 as described in Section 5.2.1.4 will apply. Starting at a 30.0 mg dose in Part B, the study will continue with a 3+3 design to identify a preliminary maximum tolerated dose (MTD). During 3+3 dose escalation in both arms, an initial cohort of 3 subjects will be enrolled to a dose level. If none of the 3 subjects experiences a DLT, escalation to the next dose will occur. If one of the 3 subjects experiences a DLT, another 3 subjects will be enrolled at this dose level. If 1 DLT is observed among the 6 subjects, the dose escalation will continue. If  $\geq 2/3$  or  $\geq 2/6$  subjects at a dose level develop DLTs, dose escalation will be terminated, and the study will proceed to the dose confirmation stage at the previous dose level. At least 2 days of observation will occur between each of the first 3 subjects at each dose level (for Part A this applies to the 2 subjects enrolled). In Part C, dose confirmation will refine the estimate of the tolerability of the MTD (or maximum administered dose), using a toxicity probability interval.

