### 5.2.1.3 Accelerated Dose Escalation (MK-1248 Monotherapy)

During the accelerated dose escalation stage (Part A), each cohort will enroll two subjects and dose escalation will proceed as designated in [Table 2](#) and [Table 3](#), until a DLT is observed or until the dose level of 10 mg is safely administered. At least 2 days of observation will occur between each of the first 2 subjects at each dose level.

If a DLT is observed during a 2-subject cohort, an additional subject will be enrolled at this dose level for a total of 3 subjects, and the rules of 3+3 dose escalation described in Section 5.2.1.4 will apply:

- If the new subject does not develop a DLT (for a total of 1/3 subjects with a DLT at that dose level), three more subjects will be enrolled at this dose level and the rules of 3+3 design (Section 5.2.1.4) will be followed for a cohort of 6 subjects. The 3+3 dose escalation design will be followed from then on with 40% increments in the dose level.
- If the new subject develops a DLT (for a total of 2/3 subjects with a DLT at this dose level), the dose escalation stage of the trial will be terminated. The third subject will be enrolled in the dose directly below the current dose and the 3+3 dose escalation design will be followed from then on with 40% increments in the dose level.

See Section 5.2.2 for definition of DLTs.

Starting with the 30 mg dose, 3 subjects will be enrolled to each dose level.

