#### 5.2.1.4 3+3 Dose Escalation (MK-1248 Monotherapy and MK-1248 plus Pembrolizumab Combination)

During MK-1248 monotherapy (Arm 1), once the 10 mg dose is safely administered, starting with the next dose the study will proceed to 3 subjects enrolled at each dose level and dose escalation continuing according to [Table 2](#). During 3+3 dose escalation, at least 2 days of observation will occur between each of the first 3 subjects at each dose level.

For MK-1248, intermediate lower dose levels, not specified in [Table 2](#) and [Table 3](#) may be investigated. This escalation schedule may be adjusted downward based on PD, PK, and safety data emerging throughout the Phase 1 study.

The rules for the preliminary MK-1248 dose finding during MK-1248 monotherapy (Arm 1) and during MK-1248 plus pembrolizumab combination treatment (Arm 2) using the 3+3 design are as follows (all dose adjustments are made only to MK-1248):

An initial cohort of 3 subjects is enrolled.

- If 0/3 subjects develops a DLT, escalation to the next dose of MK-1248 will occur.
- If 1/3 subjects develops a DLT, another 3 subjects will be enrolled at this dose level.
  - If 0 of the 3 new subjects develops a DLT (for a total of 1/6 subjects with a DLT at this dose level), escalation to the next dose level will occur.
  - If  $\geq 1$  of the 3 new subjects develop a DLT (for a total of  $\geq 2/6$  subjects with a DLT at this dose level), the dose escalation stage of the trial will be terminated. If the dose directly below the current dose had been studied in at least 3 subjects, the dose directly below the current dose will be considered the preliminary MTD, and the study will proceed to the confirmation stage. If the dose directly below the current dose had been studied in  $< 3$  subjects, more subjects to a total of 3 will be enrolled at the dose directly below the current dose before proceeding to the confirmation stage.
- If  $\geq 2/3$  subjects develop a DLT, the dose escalation stage of the trial will be terminated. If the dose directly below the current dose had been studied in at least 3 subjects, the dose directly below the current dose will be considered the preliminary MTD, and the study will proceed to the confirmation stage. If the dose directly below the current dose had been studied in  $< 3$  subjects, more subjects to a total of 3 will be enrolled at the dose directly below the current dose before proceeding to the confirmation stage.

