It is conceptually acceptable to de-escalate to an intermediate, not pre-defined and not previously-studied dose, if evaluation of toxicity at such a dose is desired in lieu of proceeding directly to the dose confirmation stage of the study. If this approach is taken, 3 new subjects should be enrolled at the new intermediate dose, and the aforementioned rules should be used to determine further enrollment at this dose level. This would be communicated to sites via administrative letter.

If the highest candidate dose of MK-1248 is studied during dose escalation, and 0/3 subjects or <2/6 subjects develop a DLT at that dose, then dose escalation will terminate with this finding and this dose level may be taken to the confirmation stage.

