#### **5.2.1.5 Dose Confirmation**

The objective of dose confirmation in Part C and Part E is to refine the estimate of the MK-1248 MTD based on TPI design [1] with target toxicity rate  $\leq 30\%$ . Dose confirmation involves the expansion of at least 1 dose level studied in the dose escalation stage of the study.

The toxicity probability interval (TPI) design [1] will be used at the dose confirmation stage. Based on the observed DLTs, the approach recommends actions of escalating, staying at, or de-escalating the dose level as presented in [Table 4](#).

Dose confirmation will begin with expansion of the preliminary MTD/MAD identified in the dose escalation stage described above. The dose confirmation part will continue until 14 subjects are studied at the selected dose (combined from dose escalation and dose confirmation) with  $\leq 5$  of 14 subjects experiencing a DLT. As subjects become evaluable for DLT assessment, the number of subjects who are evaluable for DLT versus the number of subjects who developed a DLT will be continuously assessed and de-escalation and re-escalation to eligible doses of MK-1248 will occur as shown in [Table 4](#)

The 200 mg dose of pembrolizumab will not be adjusted.

Table 4 Dose Confirmation Rules

Number of toxicities	Number of subjects treated at current dose										
	4	5	6	7	8	9	10	11	12	13	14
0	S	E	E	E	E	E	E	E	E	E	E
1	S	S	S	S	S	S	E	E	E	E	E
2	D	S	S	S	S	S	S	S	S	S	S
3	DU	D	D	S	S	S	S	S	S	S	S
4	DU	DU	DU	D	D	D	S	S	S	S	S
5		DU	DU	DU	DU	DU	D	D	S	S	S
6			DU	DU	DU	DU	DU	DU	D	D	D
7				DU	D						
8					DU						
9						DU	DU	DU	DU	DU	DU
10							DU	DU	DU	DU	DU
11								DU	DU	DU	DU
12									DU	DU	DU
13										DU	DU
14											DU

E = Escalate to the next higher dose  
 S = Stay at the current dose  
 D = De-escalate to the next lower dose  
 DU = The current dose is unacceptably toxic  
 Target toxicity rate = 30%  
 a=1; b=1; k1=1; k2=1.5; pow=1 per [1].

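### After 2/3 DLTs at a Part A dose, Section 5.2.1.3 both ends escalation and continues it in 40% steps, contrary to Sections 2.1 and 5.2.1.4, and nothing keeps those steps below the rejected dose

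*Combined protocol and SAP*

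**What the plan says.** Arm 1 opens with Part A, at 0.12, 0.6, 3 and 10 mg (Table 2). Section 5.2.1.3 describes it: "During the accelerated dose escalation stage (Part A), each cohort will enroll two subjects". If a DLT is seen, a third subject is added at that dose, "and the rules of 3+3 dose escalation described in Section 5.2.1.4 will apply". Section 2.1 agrees: "If a DLT occurs, an additional subject will be enrolled and the rules of 3+3 as described in Section 5.2.1.4 will apply".

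Two bullets in 5.2.1.3 then give the consequences. The first covers 1/3 DLTs: three more subjects at the dose, then 3+3 with 40% steps. The second covers 2/3 DLTs. It says that the escalation stage of the trial is "terminated. The third subject will be enrolled in the dose directly below the current dose and the 3+3 dose escalation design will be followed", again with 40% steps.

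Section 5.2.1.4 has its own rule for two or more DLTs in three subjects, and it uses the same termination clause: "the dose escalation stage of the trial will be terminated". If the lower dose already has three subjects, it becomes the preliminary MTD and confirmation begins. If it has fewer, "more subjects to a total of 3 will be enrolled at the dose directly below the current dose before proceeding to the confirmation stage". A Part A dose passed without a DLT has two subjects, so this second case applies. Section 2.1 likewise sends two or more DLTs in three subjects to confirmation at the previous dose level.

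**The concern.** The second bullet gives two instructions that do not fit together: escalation of the trial is over, and escalation carries on from the dose below. The lead-in points to 5.2.1.4, where the same clause means the end of escalation and a move to confirmation. A site or a sponsor team holding 2/3 DLTs at, say, 3 mg could justify either course from the text.

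The choice decides which dose enters Part C, and so bears on the first primary objective, the monotherapy MTD or maximum administered dose. It also has a safety side. If the 40% ladder is followed, the bullet does not say where it must stop relative to the dose that was just found too toxic. In a first-in-human trial the step after 2/3 DLTs should have one reading.

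**Working it through.** **Step 1: the two routes side by side, for 2/3 DLTs at a Part A dose.**

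| | 5.2.1.3, second bullet | 5.2.1.4 (with 2.1) |
|---|---|---|
| Escalation stage of the trial | terminated | terminated |
| Lower dose | bring to 3 subjects | bring to 3 subjects |
| Next | 3+3 upward in 40% steps | confirmation at the lower dose |

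The first two rows agree. The third does not.

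**Step 2: reproduce the plan's own 40% ladder.** Take dose after k steps = start × 1.4^k. Scenario 3 in Section 8.9.1 runs a 40% ladder from 3 mg to 915 mg in 18 steps. With 3 mg as the first level, the 18th is 3 × 1.4^17 = 914.7 mg, which matches.

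**Step 3: apply the ladder after a rejected Part A dose.** The start is the dose directly below. The number of steps needed to cross is log(rejected/start) / log(1.4):

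- 0.6/0.12 = 5 and 3/0.6 = 5: log 5 / log 1.4 = 4.78, so step 5 crosses.
- 10/3 = 3.33: log 3.33 / log 1.4 = 3.58, so step 4 crosses.

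| Rejected (mg) | Start (mg) | Steps below the rejected dose (mg) | First step above (mg) | Excess |
|---|---|---|---|---|
| 0.6 | 0.12 | 0.168, 0.235, 0.329, 0.461 | 0.12 × 1.4^5 = 0.645 | 7.6% |
| 3 | 0.6 | 0.84, 1.18, 1.65, 2.30 | 0.6 × 1.4^5 = 3.23 | 7.6% |
| 10 | 3 | 4.20, 5.88, 8.23 | 3 × 1.4^4 = 11.5 | 15.2% |

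The crossing step is reached only if the start dose and every step before it clear the 3+3 rules.

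**Step 4: what the routes cost in subjects.** Both add one subject at the lower dose. The 5.2.1.4 route then goes to confirmation. The ladder, even if stopped below the rejected dose, first studies 4, 4 or 3 new levels. At three subjects each that is 12, 12 or 9 subjects, and more if any level expands to six.

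**Step 5: look for a written cap.** Section 4.2.2.3 sets a planned maximum of 900 mg, and 5.2.1.4 ends escalation at the highest candidate dose. Neither is tied to a rejected dose. Section 5.2.1.4 lets the schedule be adjusted downward, and 7.1.2.1 has the sponsor and investigators review each cohort before the next opens. Both are matters of judgement, not rules that bar the rejected dose.

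**The case against.** The best defence is that the second bullet is a Part A-specific rule and that only the accelerated stage is meant to end. Sections 2.2, 5.2 and 5.2.1.2 let Part B start below 30 mg by reference to 5.2.1.3, and the note under Table 2 makes the actual doses depend on a safety-triggered switch to 40% increases. The aim is also sensible: the gaps between Part A doses are 5-fold, 5-fold and 3.3-fold, so a finer search below a rejected dose is worth having. This reading is plausible, and the fix adopts it. But the first bullet alone satisfies those cross-references, 5.2.1.3 has a separate name for the accelerated stage and does not use it here, and nothing declares an exception to 5.2.1.4.

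A second defence is that 5.2.1.4 does not force confirmation: "It is conceptually acceptable to de-escalate to an intermediate, not pre-defined and not previously-studied dose". That route is optional, is communicated by administrative letter and starts with three new subjects at a new dose. The bullet is mandatory and starts by completing an existing dose. The two are different procedures.

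A third defence stands in part. The ladder must clear each lower level before it passes the rejected dose, and each cohort is reviewed. That limits harm, but it does not supply the missing stopping point.

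A reader might go further and say that Part C should also be barred from returning to the rejected dose, since "de-escalation and re-escalation to eligible doses of MK-1248 will occur as shown in" Table 4, eligible doses are not defined, and Table 4 marks escalation at 0/5. The documents do not support calling that an error. Return towards a stopped dose is part of following 3+3 with the toxicity probability interval design, in both arms. With the plan's uniform prior, the posterior probability that the DLT rate exceeds 30% is 0.916 at 2/3. Table 4 calls a dose unacceptably toxic at 3/4 (0.969) but only de-escalates at 3/5 (0.930), so 2/3 falls short of that mark. Table 4 also says stay at 2/6, a result that stops escalation under 5.2.1.4. A ban in Part C would override Table 4 and would be a change of design.

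**Conclusion.** The text is wrong as written, and the point is minor. For 2/3 DLTs at a Part A dose, the bullet contradicts itself and conflicts with Sections 2.1 and 5.2.1.4. If the 40% ladder is the intended route, it has no written stop at the rejected dose and could reach 0.645, 3.23 or 11.5 mg. Those figures assume steps of exactly 40% from the dose directly below, with every earlier level tolerated.

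The practical effect on this trial is small. Section 4.2.2.1 reports no DLTs for the related antibody MK-4166 from 0.0015 to 10 mg, a range that covers every Part A dose, so the branch was unlikely. Enrolment closed on 31-Mar-2017. The planning figure of 96 subjects assumes no DLTs and is not touched.

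Three further inferences are not supported. The documents do not say that the branch was reached or that anyone was dosed above a rejected level. They give no DLT rates by dose, so a probability that the two routes end at different MTDs would rest on invented inputs, and none is given here. And although 0.12 mg has no listed dose below it, 5.2.1.4 allows unlisted lower doses and downward adjustment, which largely covers that case.

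**What to change.** Make three edits to the second bullet of Section 5.2.1.3:

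1. Replace the termination clause with: *the accelerated dose escalation stage (Part A) will be terminated*.
2. State that this bullet is an exception to the rule in Section 5.2.1.4 for two or more DLTs in three subjects.
3. Add: *the 40% increments will stay below the dose at which ≥2/3 subjects had a DLT*.

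The last ladder steps would then be 0.461, 2.30 or 8.23 mg after rejection of 0.6, 3 or 10 mg. Table 4 and the Part C rules stay as they are.

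The cost is protocol wording. The planned sample size, data collection and analysis do not change. With enrolment closed, the main value lies in correcting the text before it is reused in another protocol.

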#### 5.2.1.4 3+3 Dose Escalation (MK-1248 Monotherapy and MK-1248 plus Pembrolizumab Combination)

During MK-1248 monotherapy (Arm 1), once the 10 mg dose is safely administered, starting with the next dose the study will proceed to 3 subjects enrolled at each dose level and dose escalation continuing according to [Table 2](#). During 3+3 dose escalation, at least 2 days of observation will occur between each of the first 3 subjects at each dose level.

For MK-1248, intermediate lower dose levels, not specified in [Table 2](#) and [Table 3](#) may be investigated. This escalation schedule may be adjusted downward based on PD, PK, and safety data emerging throughout the Phase 1 study.

The rules for the preliminary MK-1248 dose finding during MK-1248 monotherapy (Arm 1) and during MK-1248 plus pembrolizumab combination treatment (Arm 2) using the 3+3 design are as follows (all dose adjustments are made only to MK-1248):

An initial cohort of 3 subjects is enrolled.

- If 0/3 subjects develops a DLT, escalation to the next dose of MK-1248 will occur.
- If 1/3 subjects develops a DLT, another 3 subjects will be enrolled at this dose level.
  - If 0 of the 3 new subjects develops a DLT (for a total of 1/6 subjects with a DLT at this dose level), escalation to the next dose level will occur.
  - If  $\geq 1$  of the 3 new subjects develop a DLT (for a total of  $\geq 2/6$  subjects with a DLT at this dose level), the dose escalation stage of the trial will be terminated. If the dose directly below the current dose had been studied in at least 3 subjects, the dose directly below the current dose will be considered the preliminary MTD, and the study will proceed to the confirmation stage. If the dose directly below the current dose had been studied in  $< 3$  subjects, more subjects to a total of 3 will be enrolled at the dose directly below the current dose before proceeding to the confirmation stage.
- If  $\geq 2/3$  subjects develop a DLT, the dose escalation stage of the trial will be terminated. If the dose directly below the current dose had been studied in at least 3 subjects, the dose directly below the current dose will be considered the preliminary MTD, and the study will proceed to the confirmation stage. If the dose directly below the current dose had been studied in  $< 3$  subjects, more subjects to a total of 3 will be enrolled at the dose directly below the current dose before proceeding to the confirmation stage.

It is conceptually acceptable to de-escalate to an intermediate, not pre-defined and not previously-studied dose, if evaluation of toxicity at such a dose is desired in lieu of proceeding directly to the dose confirmation stage of the study. If this approach is taken, 3 new subjects should be enrolled at the new intermediate dose, and the aforementioned rules should be used to determine further enrollment at this dose level. This would be communicated to sites via administrative letter.

If the highest candidate dose of MK-1248 is studied during dose escalation, and 0/3 subjects or <2/6 subjects develop a DLT at that dose, then dose escalation will terminate with this finding and this dose level may be taken to the confirmation stage.

#### **5.2.1.5 Dose Confirmation**

The objective of dose confirmation in Part C and Part E is to refine the estimate of the MK-1248 MTD based on TPI design [1] with target toxicity rate  $\leq 30\%$ . Dose confirmation involves the expansion of at least 1 dose level studied in the dose escalation stage of the study.

The toxicity probability interval (TPI) design [1] will be used at the dose confirmation stage. Based on the observed DLTs, the approach recommends actions of escalating, staying at, or de-escalating the dose level as presented in [Table 4](#).

Dose confirmation will begin with expansion of the preliminary MTD/MAD identified in the dose escalation stage described above. The dose confirmation part will continue until 14 subjects are studied at the selected dose (combined from dose escalation and dose confirmation) with  $\leq 5$  of 14 subjects experiencing a DLT. As subjects become evaluable for DLT assessment, the number of subjects who are evaluable for DLT versus the number of subjects who developed a DLT will be continuously assessed and de-escalation and re-escalation to eligible doses of MK-1248 will occur as shown in [Table 4](#)

The 200 mg dose of pembrolizumab will not be adjusted.

Table 4 Dose Confirmation Rules

Number of toxicities	Number of subjects treated at current dose										
	4	5	6	7	8	9	10	11	12	13	14
0	S	E	E	E	E	E	E	E	E	E	E
1	S	S	S	S	S	S	E	E	E	E	E
2	D	S	S	S	S	S	S	S	S	S	S
3	DU	D	D	S	S	S	S	S	S	S	S
4	DU	DU	DU	D	D	D	S	S	S	S	S
5		DU	DU	DU	DU	DU	D	D	S	S	S
6			DU	DU	DU	DU	DU	DU	D	D	D
7				DU	D						
8					DU						
9						DU	DU	DU	DU	DU	DU
10							DU	DU	DU	DU	DU
11								DU	DU	DU	DU
12									DU	DU	DU
13										DU	DU
14											DU

E = Escalate to the next higher dose  
 S = Stay at the current dose  
 D = De-escalate to the next lower dose  
 DU = The current dose is unacceptably toxic  
 Target toxicity rate = 30%  
 a=1; b=1; k1=1; k2=1.5; pow=1 per [1].

Subjects may be enrolled continuously (i.e., without waiting for Cycle 1 completion of subjects who have received the first dose) unless a DLT is observed at the particular dose. Once a DLT is observed, the number of subjects who are enrolled at that dose but are not yet fully evaluable for DLT assessment may not exceed the number of remaining subjects who are at risk of developing a DLT before the dose would be considered unacceptably toxic (denoted as DU in Table 4). For example, if 3/7 subjects have experienced a DLT at a given dose level, no more than an additional 2 subjects should be enrolled at this dose level until additional DLT data are available. This is because this dose level would be considered unacceptably toxic if all 2 of the additional subjects experience a DLT (i.e., 5/9 subjects with DLT in Table 4). To find out how many more subjects can be enrolled, one can count steps in diagonal direction (down and to the right) from the cell (7 subjects, 3 toxicities) to the first cell marked DU.

If enrollment expands to 14 subjects for a dose level, and  $\leq 5$  of the 14 subjects develop a DLT, then the dose confirmation will stop. If enrollment expands to 14 subjects for a dose level and  $>5/14$  subjects develop a DLT, then the next lower dose may be expanded to further explore the dose-response relationship. Note that while 30% has been the target toxicity rate used to generate the guidelines in [Table 4](#) the observed rate of subjects with DLT at the MTD may be slightly above or below 30%.

